The signatures below constitutes the approval of this protocol and the attachments and provide the necessary assurances that this trial will be conducted according to all stipulations of the protocol, including all statements regarding confidentiality, and according to local legal and regulatory requirements and applicable U.S. federal regulations, ³ ISO 14155:2020, ¹ and the Declaration of Helsinki. ²

Author & Study		
Responsible Clinician	See Electronic Signature Report	
		DATE
Medical Monitor	See Electronic Signature Report	
		DATE
Clinical Operations	C. Fl. L. S. C. D. D.	
Manager	See Electronic Signature Report	DATE
		A string
Biostatistician	Can Electronia Cionatina Deneut	
Biostatisticiali	See Electronic Signature Report	DATE
Biostatistician		
Reviewer	See Electronic Signature Report	
		DATE
Data Management	Saa Elastusuis Sisuatuus Banaut	
	See Electronic Signature Report	DATE
		No.
Medical Safety Officer	See Electronic Signature Report	
Wedien Salety Sincer	See Liethome signature Report	DATE
Approver	See Electronic Signature Report	
· · · · · · ·		DATE

CHANGE HISTORY

Version	Originator	Description of Change(s) and Section Number(s) Affected	Justification for Change	Date
1.0		Original Protocol	N/A	23 Feb 2024
2.0		Updated the primary objective in section 1.2 to match the other sections of the protocol.		12MAR2024

SYNOPSIS

Protocol Title	Evaluation of Acuvue Oasys 1-Day contact lenses in new wearers			
Sponsor	JJVC, [name]			
Clinical Phase	Clinical trial phase:			
	Post Market			
	Design control phase: Post-Marketing, Phase 4			
Trial Registration	This study will be registered on ClinicalTrials.gov by the Sponsor.			
Test Article:	Approved Product: ACUVUE OASYS® 1-DAY with HydraLuxe TM			
	TECHNOLOGY (AO1D)			
Wear and Replacement	Wear Schedule: Daily wear (DW)			
Schedules	Replacement Schedule: Daily disposable (DD)			
Objectives	Primary Objective: The primary objective of this study is to estimate the			
	incidence rate (percentage) of eyes with clinically significant slit-lamp findings (Grade 3 or 4) related to the study lens after approximately 2-weeks			
	of lens wear.			
	Exploratory Objectives: The other objectives are to measure commitment			
	to lens wear in neophyte subjects after approximately two weeks of wearing			
	experience, measure Insertion & Removal (I&R) skills, evaluate new wearer			
	confidence and motivation for lens wear, and assess lens performance (CLUE vision, comfort & handling scores).			
Study Endpoints	Primary Endpoints:			
Study Enapoints	1. Incidence (percentage) of eyes with Grade 3 or 4 slit lamp findings			
	related to the study lenses after 2-week of lens wear.			
	Exploratory Endpoints:			
	Commitment to lens wear: Do you want to continue to wear			
	contact lenses after this study? (Yes or No)			
	 Reason for discontinuation (if applicable). Time for lens insertion OU 			
	Time for lens insertion OU Time for lens removal OU			
	New wearer confidence level			
	New wearer motivation level			
	Lens performance (CLUE vision, comfort, handling scores)			
Study Design	This is a multi-site, bilateral, dispensing, non-randomized, uncontrolled,			
	unmasked, single arm study. Each subject will be fitted with the study lenses			
	and dispensed for approximately 14 days of wear.			
	There will be a total of 3 visits:			
	Visit 1: Screening, baseline evaluation and lens fitting. Dispense for 7 ± 1			
	days.			
	Visit 2: Follow up #1; Dispense an additional supply for 7 ± 1 days.			
	Visit 3: Follow up #2; Final evaluation.			
	See the flow chart at the end of the synopsis table for the schematic of the			
	study visits and procedures of main observations (Figure 1).			
Sample Size	Approximately 40 neophyte subjects will be enrolled into the study. It is			
*	anticipated that approximately 30 subjects will complete the study.			
Study Duration	The study enrollment period is approximately 8 weeks. Once enrolled,			
	subjects will be in the study for about 2 weeks, making the total study duration			
	about 10 weeks from the first subject first visit (FSFV) to last subject last visit (LSLV).			
	(LSLY).			

Anticipated Study Population	Healthy pediatric and adult subjects, ages 13 to 39 (inclusive), of any race or	
Anticipated Study Population		
	ethnicity that have never trialed or placed lenses on eye (neophytes), that meet	
E1: 11:12- C : 1 1- :	the eligibility criteria for the study.	
Eligibility Criteria - Inclusion	Potential subjects must satisfy all of the following criteria to be enrolled in the	
	study:	
	Inclusion Criteria following Screening	
	The subject must:	
	1. Read, understand, and sign the Statement of Informed Consent and	
	receive a fully executed copy of the form. (For subjects aged 18 and	
	older)	
	2. Read (or be read to) and sign the Children's Assent (Information and	
	Assent Form) and receive a fully executed copy of the form. (For	
	subjects aged 13 to 17)	
	3. Have parents or legal guardians who must read, understand, and sign	
	the Statement of Informed Consent (Parental Permission Form and	
	Authorization to Use and Disclose Medical Information). (For	
	subjects aged 13 to 17)	
	4. Appear able and willing to adhere to the instructions set forth in this	
	clinical protocol.	
	5. Be between 13 and 39 (inclusive) years of age at the time of	
	screening.	
	6. By self-report, having never worn any type of contact lenses and	
	never attempted to insert contact lenses.	
	7. Have a pair of prescription glasses on hand that corrects distance	
	vision, if determined to be required by the investigator.	
	Inclusion Criteria at Baseline Evaluation	
	8. The magnitude of the cylindrical component of the subject's vertex-	
	corrected distance refraction must be ≤ 0.75 DC in each eye.	
	9. Subject must have a vertex corrected distance sphero-cylindrical	
	refraction in the range such that appropriate spherical lens powers	
	are available for correction in both eyes. The spherical lens powers	
	available in this study are:	
	a1.00 to -6.00 (in 0.25D steps)	
	10. Best corrected monocular distance visual acuity must be 20/20 ⁻³ or	
	better in each eye.	
Eligibility Criteria –	Potential subjects who meet any of the following criteria will be excluded	
Exclusion	from participating in the study:	
	Exclusion Criteria following Screening	
	The subject must not:	
	1. Be currently pregnant or lactating.	
	2. Be currently using any ocular medications or have any ocular	
	infection of any type.	
	3. By self-report, have any ocular or systemic disease, allergies, or	
	infection, or use medications that the investigator believes might	
	contraindicate or interfere with contact lens wear, or otherwise	
	compromise the study endpoints. See section 9.1 for additional	
	details regarding systemic medications.	
	4. Have previously participated in a contact lens, contact lens primary	
	package, or lens care related clinical trial.	
	5. Be an employee (e.g., Investigator, Coordinator, Technician) or	
	immediate family member of an employee (including partner, child,	
	parent, grandparent, grandchild, or sibling of the employee or their	
	spouse) of the clinical site.	
l-	. /	

	Exclusion Criteria at Baseline Evaluation The subject must not: 6. Have clinically significant (grade 3 or higher on the FDA grading scale) slit lamp findings or other corneal, eyelid, or ocular disease or abnormalities that the investigator believes might contraindicate contact lens wear or may otherwise compromise study endpoints (including significant blepharitis, entropion, ectropion, ptosis, chalazia, recurrent styes, pterygium, significant dry eye disease, history of recurrent corneal erosions, aphakia, corneal distortion, herpetic keratitis). 7. Have a history of strabismus or amblyopia. 8. Have fluctuations in vision due to clinically significant dry eye or other ocular or systemic conditions. 9. Have had or have planned (within the study period) any ocular or intraocular surgery or procedures (e.g., PRK, LASIK, IPL, blepharoplasty, etc.)
Disallowed	See section 9.1 for details regarding disallowed systemic medications.
Medications/Interventions	
Measurements and	The key procedures associated with this study will be:
Procedures	Refraction
	Evaluation and grading of ocular physiology using a slit lamp
	biomicroscope.
	Contact lens I&R training. L&B skills measurement (a.g., time to insertion)
	I&R skills measurement (e.g., time to insertion).Contact lens fitting.
	 Evaluation of subjective comfort, vision and handling using the CLUE questionnaire.
	Evaluation of subject's confidence and motivation for lens wear (survey).
Microbiology or Other	None.
Laboratory Testing	
Study Termination	The occurrence of an Unanticipated Adverse Device Effect (UADE) or Serious Adverse Event (SAE) for which a causal relationship to a test article cannot be ruled out, could result in stopping further dispensing of the marketed product. In the event of a UADE or SAE, the Sponsor Medical Monitor may review the treatment regimen of subject(s) and may discuss this with the Principal Investigator before any further subjects are enrolled.
Ancillary Supplies/ Study- Specific Materials	BioTrue Multipurpose contact lens solution, LacriPure, Eye-Cept, or another preservative free rewetting drop. Sodium Fluorescein.
	Supply the subject a bottle of contact lens solution for rinsing purposes, if necessary.
Principal Investigator(s) and Study Institution(s)/Site(s)	A full list of Principal Investigators, clinical sites, and institutions is kept separately from the Study Protocol and is included in the study Trial Master File.
	This study will utilize approximately 5 clinical sites.

Figure 1: Study Flowchart

Visit 1: Screening

Statement of Informed Consent, Childrens Assent (if applicable)

Demographics

Medical History & Concomitant Medications

Eligibility after Screening

Visit 1: Baseline Evaluation

Subject Reported Ocular Symptoms

Baseline confidence & motivation questionnaire

Baseline (entrance) visual acuity

Spherocylindrical Refraction and Distance VA

Slit Lamp Biomicroscopy

Eligibility at Baseline

Visit 1: Lens Fitting

Lens power selection

I&R training (staff trains the subject)

I&R learning session (timed)

Lens fit assessment

Spherical over-refraction, Modification (if applicable)

Subject Reported Ocular Symptoms

Patient reported outcomes (Post fit questionnaire)

Patient education and instructions

Dispense 7± 1 days

Visit 2: Follow up #1

Wear compliance

Subject Reported Ocular Symptoms

Confidence & Motivation Questionnaire

Patient reported outcomes (Post fit questionnaire)

Removal of lenses (timed)

Slit Lamp Biomicroscopy

Insertion of lenses (timed)

Lens fit assessment

Continuance & Dispense 7± 1 days

Visit 3: Follow up #2

Wear compliance

Subject Reported Ocular Symptoms

Confidence & Motivation Questionnaire

Patient reported outcomes (Post fit questionnaire)

Removal of lenses, re-insertion of lenses (timed)

Lens fit assessment

Slit Lamp Biomicroscopy

Final Evaluation

Commitment to lens wear questionnaire

COMMONLY USED ABBREVIATIONS, ACRONYMS AND DEFINITIONS OF TERMS

ADE Adverse Device Effect

ADHD Attention Deficit Hyperactivity Disorder AE Adverse Event/Adverse Experience

AO1D ACUVUE OASYS® 1-DAY with HydraLuxe™ TECHNOLOGY

BSCVA Best Spectacle Corrected Visual Acuity

CFR Code of Federal Regulations
CLUE Contact Lens User Experience
COM Clinical Operations Manager
CRA Clinical Research Associate

CRF Case Report Form

CRO Contract Research Organization

D Diopter

DMC Data Monitoring Committee
eCRF Electronic Case Report Form
EDC Electronic Data Capture
FDA Food and Drug Administration
GCP Good Clinical Practice

HIPAA Health Insurance Portability and Accountability Act

HIV Human Immunodeficiency Virus

HL Hand Length

HVID Horizontal Visible Iris Diameter

IB Investigator's Brochure

ICH The International Council for Harmonization

IEC Independent Ethics Committee
IRB Institutional Review Board
I&R Insertion and Removal

ISO International Organization for Standardization

ITT Intent-to-Treat

JJVC Johnson & Johnson Vision Care, Inc. LASIK Laser-Assisted in Situ Keratomileusis

OD Right Eye
OS Left Eye
OU Both Eyes

MPMVA Maximum Plus to Maximum Visual Acuity

PAH Palpebral aperture height
PIG Patient Instruction Guide
PQC Product Quality Complaint
PRK Photorefractive Keratectomy
PRO Patient Reported Outcome

PW Palm Width QA Quality Assurance

SAE Serious Adverse Event/Serious Adverse Experience

SAP Statistical Analysis Plan
SAS Statistical Analysis System
SD Standard Deviation

UADE Unanticipated Adverse Device Effect
USADE Unanticipated Serious Adverse Device Effect

VA Visual Acuity

1. INTRODUCTION AND BACKGROUND

1.1. Name and Descriptions of Investigational Products

This study will use the commercially available spherical ACUVUE OASYS® 1-DAY with HydraLuxeTM TECHNOLOGY (AO1D) contact lenses. Further details about the Test article are found in section 6 of this protocol.

1.2. Intended Use of Investigational Products

The intended use of the study lenses is for correcting myopia. There will be one treatment in this study. During the study, subjects will wear AO1D lenses bilaterally in daily wear, daily disposable modality over the course of approximately two weeks. Since the primary objective of this study is to estimate the incidence rate (percentage) of eyes with clinically significant slit-lamp findings (Grade 3 or 4) related to the study lens after approximately 2-weeks of lens wear, subjects will not be required to adhere to any specific minimum lens wear requirements, however, they will be instructed to only wear the lenses during waking hours and educated on typical wear time (e.g., maximum 14-16 hours per day).

1.3. Summary of Findings from Nonclinical Studies

Not Applicable – Marketed product only.

1.4. Summary of Known Risks and Benefits to Human Subjects

The following risks/adverse events and clinical benefits can be associated with wearing soft contact lenses in general:

- The eyes may burn, sting and/or itch.
- There may be a feeling of something in the eye (foreign body, scratched area).
- There may be the potential for some temporary impairment due to peripheral infiltrates, peripheral corneal ulcers, and corneal erosion.
- There may be the potential for other physiological observations, such as local or generalized edema,
- corneal neovascularization, corneal staining, injection, tarsal abnormalities, iritis and conjunctivitis, some of which are clinically acceptable in low amounts.
- There may be excessive watering, unusual eye secretions, or redness of the eye.
- Poor visual acuity, blurred vision, rainbows or halos around objects, photophobia, or dry eyes may also
 occur.
- Soft contact lenses, like spectacle lenses, provide correction of refractive error.

For the most comprehensive risk and benefit information regarding study lenses refer to the package insert of the marketed product (Appendix C).

1.5. Relevant Literature References and Prior Clinical Data Relevant to Proposed Clinical Study

Recent review of the literature points to several factors that may contribute to new wearer dropout. Sulley *et al* found that the main reasons for discontinuation were problems with vision (41%), discomfort (36%), and handling problems $(25\%)^4$.

This study will measure commitment to lens wear in a healthy neophyte population. Eligible subjects will be trained and fitted into a commercially available daily disposable contact lens brand (AO1D), known for its acceptable clinical performance. After approximately two weeks of wear experience, subjects will be interviewed about their commitment to lens wear. Subjects may drop out of the study prematurely, and if so, the reason for dropping out will be documented.

For the most comprehensive information regarding study lenses refer to the package insert of the marketed product (Appendix C).

2. STUDY OBJECTIVES, ENDPOINTS AND HYPOTHESES

2.1. Objectives

Primary Objective: The primary objective of this study is to estimate the incidence rate (percentage) of eyes with clinically significant slit-lamp findings (Grade 3 or 4) related to the study lens after approximately 2-weeks of lens wear.

Exploratory Objectives: The other objectives are to measure commitment to lens wear in neophyte subjects after approximately two weeks of wearing experience, measure Insertion & Removal (I&R) skills, evaluate new wearer confidence and motivation for lens wear, and assess lens performance (CLUE vision, comfort & handling scores).

2.2. Endpoints

Primary Endpoint:

1. Percentage of eyes with slit-lamp findings (Grade 3 or 4) related to study lens wear:

Slit Lamp Findings (Grade 3 or higher) will be assessed for each subject eye at all study visits (scheduled and unscheduled). However, the primary endpoint will be the percentage of eyes with Grade 3 or higher SLFs related to study lens wear, after approximately 2 weeks of lens wear. SLFs will be evaluated and classified using the FDA Grading scale rating from 0 to 4, where Grade 0 represents the absence of findings and 1 to 4 representing successively worse findings (i.e., Grade 1=trace, Grade 2= mild, Grade 3=moderate and Grade 4= severe).

Other Exploratory Endpoints:

- 1. **Commitment to lens wear:** Do you want to continue to wear contact lenses after this study? (Response set: Yes, No)
- 2. **Reasons for Discontinuation** (if applicable): Which of the following is the main reason why you want to **stop** wearing contact lenses? (Response set: They were uncomfortable to wear, My eyes were too dry to wear them, I didn't like my vision with contacts, They were too difficult to put on and take off, They were more trouble than it's worth, I'm concerned about the cost, and Other reason [free text])

3. **Insertion Time:**

Insertion time is quantified as the total time (in minutes and seconds) it takes for the subject to insert both lenses (OU). Insertion time will be collected at the initial fitting, after approximately 1-week of wear, and after approximately 2-weeks of wear. The insertion time is a continuous endpoint.

4. Removal Time:

Removal time is quantified as the total time (in minutes and seconds) it takes for the subject to remove their lenses (OU) at three different time points – at the initial fitting, after approximately 1-week of wear, and after approximately 2-weeks of wear. The removal time is a continuous endpoint.

5. Confidence:

New wearer **confidence** (**for lens wear**) will be assessed at baseline (prior to lens fitting), post fitting, after approximately 1-week of wear, and after approximately 2-weeks of wear using the individual questionnaire item: How confident do you feel in your ability to successfully **put on** contact lenses? (Response Set: Not confident, A little confident, Somewhat confident, Confident, Highly confident). (Response Set: No confidence/Little Confidence/Some Confidence/Confident/High Confidence). New wearer confidence is an ordinal categorical endpoint.

6. Motivation:

New wearer motivation (for lens wear) will be assessed at baseline (prior to lens fitting), post lens fitting, after approximately 1-week of wear, and after approximately 2-weeks of wear using the individual questionnaire item: How motivated are you to wear contact lenses? (Response Set: I am not

motivated, /I am a little motivated, /I am somewhat motivated, /I am motivated, /I am highly motivated). New wearer motivation is an ordinal categorical endpoint.

7. **CLUE Vision, Comfort, and Handling scores** will be collected at the initial fitting, after approximately 1-week of wear, and after approximately 2 weeks of wear. The CLUE vision, comfort and handling scores are continuous endpoints.

Subjective comfort, vision, handling scores will be assessed using the Contact Lens Use Experience (CLUETM)⁵ questionnaire after approximately 30 minutes of lens wear (post initial fitting), and after approximately 1 and 2 weeks of wear. CLUE is a validated patient-reported outcomes questionnaire to assess patient-experience attributes of soft, disposable contact lenses (comfort, vision, handling, and packaging) in a contact-lens wearing population in the US. Derived CLUETM scores using Item Response Theory (IRT) follow a normal distribution with a population average score of 60 (SD 20), where higher scores indicate a more favorable/positive response with a range of 0-120. A 5-point increase in an average CLUETM score translates into 10% shift in the distribution of scores for population of soft contact lens wearers.

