14. STATISTICAL METHODS

14.1. General Considerations

Statistical analysis will be undertaken by the study biostatistician. A general description of the statistical methods to be implemented in this clinical trial is outlined below.

All data summaries and statistical analyses will be performed using the SAS software Version 9.4 or higher (SAS Institute, Cary, NC⁶. Throughout the analysis of data, the results for each subject/eye will be used when available for summarization and statistical analysis. Unscheduled visits will be summarized separately and will be excluded from the statistical analysis.

Summary tables (descriptive statistics and/or frequency tables) will be provided for all baseline variables, efficacy variables, and safety variables as appropriate. Continuous variables will be summarized with descriptive statistics

(n, mean, standard deviation [SD], median, minimum and maximum). Frequency count and percentage of subjects or eyes within each category will be provided for categorical data.

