14.5. Primary Analysis

The primary analyses will be conducted on the safety population. The primary endpoint will be summarized using counts and percentages. The primary endpoints will be evaluated using the following clinical findings:

Incidence (percentage) of eyes with Grade 3 or 4 slit lamp findings related to the study lenses after 2-week of lens wear.

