14.9. Procedure for Handling Missing Data and Drop-Outs

Missing or spurious values will not be imputed. The count of missing values will be included in the summary tables and listings.

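### The primary safety incidence is really a status at about 2 weeks: related Grade 3/4 findings that resolve before Visit 3 drop out, and the plan does not say whether early-exit exams count

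*Combined protocol and SAP*

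**What the plan says.** Section 2.1 sets the primary objective as to "estimate the incidence rate (percentage) of eyes with clinically significant slit-lamp findings (Grade 3 or 4) related to the study lens" after about two weeks of wear. The synopsis and section 1.2 carry matching wording. Section 14.5 takes the Safety population and names the quantity as "Incidence (percentage) of eyes with Grade 3 or 4 slit lamp findings related to the study lenses after 2-week of lens wear".

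Section 2.2 first says that Grade 3 or higher findings are assessed in each eye at every visit, scheduled or not. The next sentence opens with *However* and narrows this: "the primary endpoint will be the percentage of eyes with Grade 3 or higher SLFs related to study lens wear, after approximately 2 weeks".

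Three further provisions bear on which data enter:

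- Section 14.1: "Unscheduled visits will be summarized separately and will be excluded from the statistical analysis". It also says that "the results for each subject/eye will be used when available for summarization and statistical analysis".
- Section 14.9: nothing is imputed, and "The count of missing values will be included in the summary tables and listings".
- Section 7.2, step F.4: subjects who discontinue early get an exit slit-lamp exam, unless they were screen failures or biomicroscopy has just been done. Nothing links this exam to the primary endpoint.

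**The concern.** An incidence over two weeks of wear should count every eye that develops the finding during those two weeks. A status at one visit counts only eyes that show it on that day. The plan uses the first name for the second quantity.

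The event can also remove a subject before the counting day. Section 13.1 lists Grade 3 or higher corneal findings among the significant adverse events. Section 8.2 withdraws subjects whose significant event necessitates even temporary discontinuation of lens wear. Eyes that meet the endpoint early are therefore among those that may have no Visit 3 exam.

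No hypothesis is tested, so the descriptive percentage is the whole primary result. If it omits eyes affected earlier, a reader who takes it as the two-week incidence is misled.

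**Working it through.** **1. Which visit is the 2-week time point.** Table 3 puts Visit 2 at 7 ± 1 days after Visit 1 (day 6 to 8) and Visit 3 at 7 ± 1 days after Visit 2. Visit 3 therefore falls between day 6 + 6 = 12 and day 8 + 8 = 16. Section 2.2 treats one and two weeks as separate time points for other endpoints: "Insertion time will be collected at the initial fitting, after approximately 1-week of wear, and after approximately 2-weeks of wear". So two weeks means Visit 3 and does not include Visit 2.

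**2. Which exams feed the primary percentage as written.**

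| Slit-lamp exam | Where | In the primary figure? |
|---|---|---|
| Visit 1 learning session (optional) | 7.2, step 1.18 | No: before week 2 |
| Visit 2 | 7.2, step 2.12 | No: week 1 |
| Unscheduled visit | 7.3, step U.6 | No: by timing if early, by 14.1 if near week 2 |
| Visit 3 | 7.2, step 3.14 | Yes |
| Early-exit exam | 7.2, step F.4 | Not stated |

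No section says that an eye counts if it was affected at any exam up to two weeks.

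**3. Denominator.** It is not written out. Sections 14.1 and 14.9 point to Safety-population eyes with data, with the missing count shown.

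**4. Inputs for an illustration.** The plan states no event rate and no expected value of the primary percentage, so there is no figure of its own to reproduce. Sections 4.3 and 14.2 give about 40 enrolled and about 30 completing. I assume all 40 are exposed to the lens and 30 reach Visit 3, which gives 30 × 2 = 60 eyes. The 40 is only a target: enrollment is counted at consent, so screen failures may be among them, and leavers may be replaced.

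Let V = eyes affected at Visit 3, E = eyes affected only earlier, and D = eyes with at least one post-exposure exam. With k early leavers examined, D = 60 + 2k: 64 for k = 2 and 80 for k = 10. Compare V/60 with (V + E)/D.

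- **A. Two completer eyes affected at Visit 2, resolved by Visit 3 (V = 0, E = 2).** Visit 3: 0/60 = 0%. Any exam: 2/60 = 3.3% over the same eyes, or 2/80 = 2.5% if all 10 leavers were also examined. This does not depend on F.4.
- **B. The two affected eyes belong to two subjects who exit.** If F.4 does not count: 0/60 = 0% against 2/64 = 3.1% to 2/80 = 2.5%. If F.4 counts and the finding is still present, nothing is lost.
- **C. One eye affected at Visit 3 and none earlier (V = 1, E = 0).** Visit 3: 1/60 = 1.7%. Any exam: 1/64 = 1.6% to 1/80 = 1.25%. Here the Visit 3 figure is the higher one.

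**5. Direction.** Over one fixed set of n eyes, V/n ≤ (V + E)/n always. With different denominators, setting V/60 = (V + E)/D gives E/(V + E) = 1 − 60/D. That is 0% at D = 60, 6.25% at D = 64 and 25% at D = 80. Check at D = 80 with V = 3 and E = 1: 3/60 = 4/80 = 5%. The Visit 3 figure understates once early-only eyes exceed that share of all affected eyes.

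**The case against.** The strongest reply is that the time point is deliberate. The synopsis and sections 1.2, 2.1, 2.2 and 14.5 all say about two weeks, and *However* shows that the all-visit option was seen and set aside. Status at two weeks is a legitimate endpoint. On that view only the label needs correcting.

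Early events are not lost either. A Grade 3 finding at Visit 2 is recorded as an adverse event, significant events reach the sponsor within 24 hours, and unscheduled visits are summarized separately. There is no hypothesis test, interim analysis or planned publication, and the lens is already marketed.

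Scenario A is also narrow. It needs a subject to stay in with a related Grade 3 finding that then resolves within about a week. Section 13.3 leaves continuation to the investigator's judgment, so this can happen, but the withdrawal rules in 8.2 would turn many such eyes into early exits.

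Much of this stands as fact, and it limits the size of the problem. It does not make a one-visit status answer an objective stated as incidence. If someone instead reads the wording as cumulative, two analysts could report different primary results from the same data, and the same clarification is needed.

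A reader might go further and infer that every finding in a subject who exits early is excluded. The documents do not support that. Section 14.1 excludes unscheduled visits and does not mention exit exams, the Safety population includes early leavers, and results are used when available. The position of F.4 is open.

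**Conclusion.** The point holds in a limited form and should be fixed. As written, a related Grade 3 or 4 finding that appears at Visit 2 or at an earlier unscheduled visit and resolves before Visit 3 is left out of a figure called an incidence. For early exits, inclusion is undefined. That matters because the endpoint event can itself lead to exit.

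The size cannot be derived from the documents. The illustrated gaps of 2.5 to 3.3 percentage points for two eyes rest on assumed counts (60 eyes at Visit 3, and up to 80 examined). A reader might also infer that the primary figure must be too low. That is not supported: over the same eyes it can only equal or fall below the any-exam figure, but with different denominators it can be higher, as scenario C shows. Nor are early findings hidden from the study report; they are only outside the primary percentage.

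**What to change.** In 2.2 and 14.5, and in the matching wording of the synopsis, 1.2 and 2.1, define the primary incidence as eyes with at least one related Grade 3 or 4 finding at any slit-lamp exam from first exposure to the study lens through Visit 3 or exit. Count Visit 1 learning-session exams, Visit 2, Visit 3, unscheduled visits and F.4. Starting at first exposure matches the Safety population (14.3) and the start of adverse-event recording (13.3).

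In 14.1, exempt slit-lamp findings from the unscheduled-visit exclusion.

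Use as denominator the Safety-population eyes with at least one post-exposure exam. Report the number of exposed eyes with none, and also show the percentage over all Safety-population eyes. Keep the Visit 3 percentage as a supportive table, labelled as a 2-week proportion.

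The cost is wording only; no exam or visit is added. The downsides are that the figure may be less favourable and that it mixes scheduled with symptom-triggered exams, which the supportive Visit 3 table lets a reader judge. Eyes with no post-exposure exam remain unknown, which is why their number is reported.
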